2.6.11 MSCs in Other Neurologic Conditions

A few clinical trials of autologous MSC therapy have been conducted in patients with multiple sclerosis. Of 25 patients with progressive multiple sclerosis treated with a single intrathecal injection of autologous bone marrow-derived MSCs, the disease stabilized in half of patients over a one-year time period.⁷⁵ Side effects, all transient and self-limited including low-grade fever, nausea/vomiting, lower limb weakness, and headache, were likely related to the intrathecal route of administration and were consistent with those reported from other small studies of intrathecal MSC treatment in patients with multiple sclerosis.^{76,77} Another study that treated 10 patients with progressive visual deficits due to multiple sclerosis with a single intravenous dose of autologous bone marrow-derived MSCs demonstrated improvements in visual acuity, visual evoked response latency, and optic nerve area.⁷⁸

One clinical trial has been conducted in seven patients with Parkinson's Disease who received a single dose of autologous bone marrow-derived MSCs transplanted to the subventricular zone using stereotaxic surgery. With a follow-up of 10 to 36 months, three patients demonstrated an improvement in disease symptoms. Two patients also reported subjective improvement of symptoms and reduction in drug dosage.⁷⁹

2.7 Source of Unrelated CB Units for this Trial

The Carolinas Cord Blood Bank (CCBB) is one of the largest public cord blood banks in the nation. Established in 1998 with support from the National Heart and Blood Institute of the NIH, the CCBB has over 30,000 CB units in inventory and has distributed over 2,500 CB units for transplant to date. In 2012 the CCBB received approval from the FDA for its BLA application to market DUCORD, a stem cell product derived from umbilical cord blood, for use in transplants between unrelated donors and recipients. DUCORD is approved for use in hematopoietic stem cell reconstitution for patients with disorders affecting the hematopoietic system that are inherited, acquired, or result from myeloablative treatment. The CCBB currently collects from 10 hospital sites (8 in North Carolina, 1 in Atlanta, GA and 1 in Boston, MA). It also accepts CB donations from mothers delivering in any hospital in North Carolina and Atlanta through a kit donation program.

2.8 Specifications for Qualification CB Units

Based on established criteria utilizing allogeneic CB for hematopoietic stem cell transplantation and our experience in treating more than 600 children with autologous CB for neurological conditions, we have established the following criteria to qualify banked CB units for cell therapy studies. CB units utilized for this current study will be obtained from the Carolinas Cord Blood Bank. It is the first choice to utilize CB units from the Carolinas Cord Blood Bank. However, if a qualifying CB unit cannot be found from the Carolinas Cord Blood Bank, another accredited bank may be used to locate a matching CB unit with the following criteria listed below:

The CB unit must have:

- 1. Pre-cryopreservation total nucleated cell count (TNCC) documented and at least 12×10^{7} /kg. We target CB units that are at least 12×10^{7} /kg, however, we will accept units that are at least 10×10^{7} /kg.
- 2. Pre-cryopreservation viability ≥85% of total cells and ≥70% of CD34+ cells (if performed)
- 3. Pre-cryopreservation sterility culture performed and negative

- 4. Maternal infectious disease screening as follows: Testing must include negative results for Hepatitis B, Hepatitis C, HIV, HTLV, and syphilis. Additional screening, which is dependent on the timing of the CB collection, may be performed based on local and national regulations. Units from mothers who have a positive CMV antibody screen may be used.
- 5. Test sample available for identity confirmation and potency testing
- 6. HLA typing performed and meets study-specific parameters
- 7. CD45+ viability ≥40% and CD34+ viability ≥70% on thawed test sample

These same criteria will be utilized for this clinical trial and, along with procedures for CB administration, are detailed again in section 6.0.

2.9 Source of MSCs for this Study: hCT-MSC

hCT-MSC is a third party MSC product manufactured from allogeneic donor digested umbilical cord tissue that is expanded for two passages in culture, cryopreserved, stored in the vapor phase of liquid nitrogen, and banked. The umbilical cord tissue is donated by healthy mothers delivering healthy full term babies after a normal pregnancy with written informed consent. The cells are manufactured, cryopreserved and stored in the Robertson CT2 GMP laboratory (Duke University, Durham, NC).

Umbilical cord tissue is an attractive source of MSCs as it is readily available and easily obtained without consequence to the donor, is non-controversial, has a higher proliferative potential than MSCs from other postnatal sources.⁸⁰ Numerous preclinical studies have not demonstrated any evidence of tumorigenicity or toxicity of cord tissue-derived MSCs.⁸¹ A summary of early phase clinical trials published in English that utilized cord tissue-derived MSCs is shown in Table 1. Among these 36 studies including 695 patients and at least 1,416 doses of cord tissue-derived MSCs with follow-up ranging from three months up to six years, no severe adverse events were reported. Several more clinical trials of cord-tissue derived MSCs in various disease conditions are underway (clinicaltrials.gov).

Table 1:	Umbilical Cord	Tissue-Derived	MSCs Studied in Humans
----------	-----------------------	-----------------------	------------------------

Report	Indication	# of treated patients	Ages, yr (range or mean)	Route of administration	Dose	# of doses (interval)	Duration of f/u (months)	AEs due to CT-MSCs
Li, 2016 ^{74,82}	Autism	20	3-14	IT	1x10 ⁶ /kg	2 (5-7 days)	6	transient fever (n=4)
Xie, 2016 ⁸³	Hypoxic Ischemic Encephalopathy	12	45-68	IV	1x10 ⁸	1	6	none
Wang, 2016 ⁸⁴	Juvenile Idiopathic Arthritis	10	2-15	IV	4x10 ⁷	2 (3 months)	12	none
Chen, 2016 ⁸⁵	Psoriasis	2	26-35	IV	1x10 ⁶ /kg	1, 5	48, 60	none
Cai, 2016 ³⁴	Type I Diabetes	21	5-28	Intra-arterial (pancreatic artery)	1.1x10 ⁶ /kg	1	12	none
Hu, 2016 ⁸⁶	Type 2 Diabetes	31	42-63	IV	1x10 ⁶ /kg	2 (monthly)	36	none
Hua, 2016 ⁸⁷	Spinal Cord Injury	1	25	IT	1x10 ⁷	4 (3 days)	12	none
Kim, 2016 ⁸⁸	Atopic Dermatitis	34	29	Subcutaneous	2.5-5x10 ⁷	1	3	none
Qin, 2016 ⁸⁹	Diabetic Foot	28	N/A	Endovascularly	N/A	N/A	3	none
Wang, 2016 ^{90,91}	Lupus	40	17-54	IV	1x10 ⁶ /kg	2 (weekly)	12-72	none
Zhao, 2015 ⁹²	Heart Failure	30	53.2	Intracoronary	NR	1	6	none
Liang, 2015 ⁹³	Radiation Myelitis	1	37	IV, IT	5.2x10 ⁷ IV, 1.1x10 ⁷ IT	1	18	none
Wang, 2015 ⁷¹	Cerebral Palsy	16	4-12	IT	1-1.5x10 ⁷	4	6	NR
Li, 2015 ⁹⁴	Coronary Artery Occlusion	15	N/A	Intracoronary	3-5x10 ⁶	1	24	none
Rajput, 2015 ⁹⁵	Duchenne Muscular Dystrophy	11	5-18	IV & IM	1x10 ⁶ /kg	4 (monthly)	36	none
Gu, 2015 ⁹⁶	Lupus Nephritis	58	12-55	IV	1x10 ⁶ /kg	1	12	none
Pan, 2015 ⁹⁷	Bone Marrow Necrosis	1	11	Intrabone	2x10 ⁷	1	38	none
Wu, 2015 ⁹⁸	GvHD	24	14-44	IV	0.5-1x10 ⁶ /kg	1	1-24	none
Zhu, 2015 ⁹⁹	Leukemia, undergoing haplo HSCT	25	4-17	IV	1-1.4x10 ⁶ /kg	1	3-25	none
Miao, 2015 ¹⁰⁰	Neurological disorders	88	2-68	IT	NR	4-6 (5-7 days)	NR	transient HA, fever, back/leg pain

Report	Indication	# of treated patients	Ages, yr (range or mean)	Route of administration	Dose	# of doses (interval)	Duration of f/u (months)	AEs due to CT-MSCs
Li, 2015 ¹⁰¹	Becker Muscular Dystrophy	3	6-46	IV	3-5x10 ⁷	1	3	none
Wang, 2015 ¹⁰²	Hemorrhagic Cystitis	7	11-38	IV	0.8- 1.6x10 ⁶ /kg	1-3	NR	none
Cheng, 2014 ¹⁰³	Spinal Cord Injury	10	35.3	Spinal Cord Injection	2x10 ⁷	2 (10 days)	6	none
Chang, 2013 ³⁶	Bronchopulmonary Dysplasia	9	10 days	Intratracheal	1-3x10 ⁷	1	3	none
Li, 2014 ¹⁰⁴	Multiple Sclerosis	13	42	IV	4x10 ⁶ /kg	3 (2 weeks)	12	none
Kong, 2014 ¹⁰⁵	Type 2 Diabetes	18		IV	N/A	3	6	slight fever
Wang, 2013 ¹⁰⁶	Traumatic Brain Injury	20	5-48	IT	1x10 ⁷	4 (5-7 days)	6	HA, dizziness
Wang, 2013 ¹⁰⁷	Primary Biliary Cirrhosis	7	33-58	IV	0.5x10 ⁶ /kg	3 (monthly)	12	none
Zhang, 2013 ¹⁰⁸	HIV	7	26-49	IV	0.5x10 ⁶ /kg	3 (monthly)	12	none
Jin, 2013 ¹⁰⁹	Spinocerebellar Ataxia	16		IV & IT	N/A	N/A	12	none
Wu, 2013 ¹¹⁰	Leukemia, undergoing CBT	8	3-12	IV	2-10x10 ⁶ /kg	1	8-27	none
Jiang, 2013 ¹¹¹	Stroke	4	40-59	Intra-arterial (MCA)	2x10 ⁷	1	6	none
Hu, 2013 ³⁵	Type I Diabetes	15	17.6	IV	1.5-3.2x10 ⁷	1	24	none
Shi, 2012 ¹¹²	Liver Failure	24	24-59	IV	0.5x10 ⁶ /kg	3 (monthly)	18	none
Zhang, 2012 ¹¹³	Liver Cirrhosis	30	25-64	IV	0.5x10 ⁶ /kg	3 (monthly)	12	none
Qu, 2009 ¹¹⁴	Bone Nonunion	36	36	Intrabone	1x10 ⁶ - 1x10 ⁷	1	13	none
Totals: 36 studies		695	0-68	IV: 362 IT: 162 Other: 199		>1,416	3-72	4 studies (3 IT route)

Abbreviations: HA-headache, IM-intramuscular, IT-intrathecal, IV-intravenous, N/A-not available, NR- not recorded

2.10 Study Rationale and Hypotheses

As described above, previous studies suggest that adequately dosed autologous CB infusion can improve motor function in children with cerebral palsy. As it is not feasible that every child with cerebral palsy will have access to their autologous CB, this study will assess efficacy of two allogeneic sources of cells that can be available to all patients in need. The major goal of this study is to investigate change in motor function 12 months after treatment with two allogeneic cell sources, allogeneic CB and hCT-MSCs. This study will generate important data regarding the effect size of change in motor function of these two cell sources and a natural history cohort to aid in the planning of future trials. The rationale for the study and for the potential benefit of cell therapy in cerebral palsy is based upon the following hypotheses:

- We have demonstrated safety and preliminary evidence of potential dose-dependent efficacy of autologous CB infusions in children with cerebral palsy.
- It is possible that different cell types, e.g. cord blood mononuclear cells versus cord tissue MSCs, may influence brain connectivity by different mechanisms.
- Multiple doses of cells may be superior to a single dose of cells.
- The developing brain exhibits remarkable plasticity, making young children ideal candidates for deriving maximal therapeutic benefit from restorative therapies, including CB.
- CB cells, acting through paracrine mechanisms, may facilitate endogenous repair mechanisms and promote formation of new neural connections the motor cortex resulting in significant clinical improvements.
- Brain connectivity plays an important role in the pathophysiology, and potentially mechanism of repair, of brain injury in children with cerebral palsy. Specifically, we hypothesize that (1) impairments in brain connectivity account for the motor deficits in children with cerebral palsy, (2) increases in brain connectivity have a direct impact on functional improvements, (3) children with cerebral palsy who receive CB infusions will exhibit greater increases in brain connectivity than children who receive placebo infusions, and (4) the severity of baseline brain connectivity abnormalities predict the potential for benefit of CB therapy.

2.11 Study Design

This study is a phase I/II, prospective, randomized, open-label trial designed to assess the effect size of change in GMFM-66 score in subjects treated with hCT-MSC or allogeneic CB and assess the safety of repeated doses of hCT-MSC in young children with cerebral palsy. Children ages 2-5 years with cerebral palsy due to hypoxic ischemic encephalopathy, stroke, or periventricular leukomalacia may be eligible to participate. All participants will ultimately be treated with an allogeneic cell product at some point during the study. Participants will be randomized to one of three arms: (1) the "AlloCB" arm will receive one allogeneic CB infusion at the baseline visit; (2) the "MSC" arm will receive three hCT-MSC infusions, one each at baseline, three months, and six months; (3) the "natural history" arm will not receive an infusion at baseline but will receive an allogeneic CB infusion at 12 months. All participants will have an initial clinical evaluation to verify and classify the diagnosis of cerebral palsy and determine eligibility. They will return for study visits an additional two (AlloCB and natural history arms) or three (MSC arm) times. Outcome measures, described in detail in section 7.6, will be assessed at baseline, six-months, and one-year time points. Additional safety endpoints will be assessed remotely for 12 months after the final in-person visit.

2.12 Risks and Benefits

CB cells will be thawed, washed, and infused using standard operating procedures that have been used in over 35,000 individuals worldwide. The potential risks associated with infusion of allogeneic CB cells include a hypersensitivity reaction to the product (rash, shortness of breath, wheezing, difficulty breathing, hypotension, swelling around the mouth, throat or eyes, tachycardia, diaphoresis) to the product or transmission of infection. Additional risks associated with infusion of allogeneic CB cells include hypertension, bradycardia, anaphylaxis, hematuria, acute hemolytic reaction, rejection of cells, immune dysregulation (develop of HLA directed antibodies), and development of graft-versus-host disease. All CB units are screened for the risk of transmitting infectious agents and must meet release criteria prior to infusion, as described below. Participants must have normal immune function and will not receive immunosuppressive therapy prior to or after infusion of CB or hCT-MSC.

Potential risks associated with MSC infusion include a reaction to the product (rash, shortness of breath, wheezing, difficulty breathing, hypotension, swelling of the mouth, throat or eyes, tachycardia, diaphoresis), infection transmission, and HLA sensitization. Theoretical risks that must be considered but have not been associated with MSC administration include the possibility of immune suppression and ectopic tissue formation. CB collected with the cord tissue used to manufacture hCT-MSC is screened for the risk of transmitting infectious agents, and the product must meet release criteria prior to infusion, as described below. Participants must have normal immune function and will not receive immunosuppressive therapy prior to or after infusion of hCT-MSC.

Participants who undergo a brain MRI may require moderate sedation or, rarely, general anesthesia, in order to complete the MRI and infusion. Risks associated with anesthesia include nausea, vomiting, blood vessel injury, nerve injury, lung injury, heart attack, allergy to medications, brain damage, respiratory insufficiency, hypoxia, hypotension, and anaphylaxis, and death. These associated risks are described in detail in the consent form. Risks associated with blood draws and IVs include momentary discomfort or pain, bruising, infection, bleeding, clotting, and fainting. Risks associated with genetic testing include medical, psychosocial, and economic risks, effects on insurability and employability, limits on educational options, and social stigma.

Potential benefits of this intervention include the possibility that the cells may, via direct or indirect mechanisms, induce changes *in vivo* that result in motor improvement.

3.0 STUDY OBJECTIVES

Primary Objective: To determine the effect size of change in GMFM-66 score in children with cerebral palsy treated with a single dose of approximately 10×10^7 cells/kg of allogeneic CB or three doses of 2×10^6 cells/kg of hCT-MSC.

Secondary Objective: To assess the safety of repeated doses of hCT-MSC in children with cerebral palsy.

Exploratory Objectives: (1) To determine the change in the Peabody Developmental Motor Scale-2 (PDMS-2) score at 6 and 12 months in children treated with allogeneic CB or hCT-MSC. (2) To analyze the change in normalized total brain connectivity, as measured by brain MRI with DTI, from baseline to 12 months. (3) To assess changes functional and quality of life measures at 6 and 12 months.

4.0 STUDY DESIGN

4.1 General Design

This study is a phase I/II, prospective, randomized, open-label trial designed to determine the effect size of change in GMFM-66 score in subjects treated with hCT-MSC or allogeneic CB and assess the safety of repeated doses of hCT-MSC in children with cerebral palsy. Children ages 2-5 years with cerebral palsy due to hypoxic ischemic encephalopathy, stroke, or periventricular leukomalacia may be eligible to participate. All participants will ultimately be treated with an allogeneic cell product at some point during the study. Participants will be randomized to one of three arms: (1) the "AlloCB" arm will receive one allogeneic CB infusion at the baseline visit; (2) the "MSC" arm will receive three hCT-MSC infusions, one each at baseline, three months, and six months; (3) the "natural history" arm will not receive an infusion at baseline but will receive an allogeneic CB infusion at 12 months. Motor outcome measures will be assessed at baseline, six-months, and one-year time points. Safety will be evaluated at each infusion visit and remotely for an additional 12 months after the final visit. Duration of study participation will be 24 months from the time of baseline visit. Randomization to treatment arms will be stratified by GMFCS level at study entry and etiology of CP (Stroke vs. Other).

4.2 Study Flow Chart

*MRI will be performed in a subset of participants

4.3 Study Endpoints

Primary Endpoint:

The primary endpoint is the difference between a participant's observed and expected changes in GMFM-66 score 12 months after the initial study infusion. Interval estimates will be reported separately for the hCT-MSC, AlloCB, and Natural History arms. Expected GMFM-66 scores at 12 months will be calculated based on the participant's baseline age, GMFCS level, and GMFM-66 score at study entry using published reference percentiles.⁶⁴

Secondary Endpoints:

The secondary endpoint is the number of adverse events occurring over the 12-month period post-infusion with hCT-MSC or AlloCB.

Exploratory Analyses:

- Observed GMFM-66 score at baseline, 6, and 12 months
- Change in the Peabody Developmental Motor Scale-2 (PDMS-2) score at 6 and 12 months.
- Change in normalized total brain connectivity, as measured by brain MRI with DTI, from baseline to 12 months.
- Change in functional and quality of life measures at 6 and 12 months.

5.0 RESEARCH PARTICIPANT SELECTION AND WITHDRAWAL

5.1 Study Population

Ninety evaluable children ages 2-5 years with hypertonic cerebral palsy.

5.2 Inclusion Criteria

- 1. Age \geq 24 months and \leq 60 months adjusted age at the time of enrollment.
- 2. Diagnosis: Unilateral or bilateral hypertonic cerebral palsy secondary to in utero or perinatal stroke/hemorrhage, hypoxic ischemic encephalopathy (including, but not limited to, birth asphyxia), and/or periventricular leukomalacia.
- 3. Performance status: Gross Motor Function Classification Score levels I IV
- 4. Review of brain imaging (obtained as standard of care prior to study entry) does not suggest a genetic condition or brain malformation.
- 5. Legal authorized representative consent.

5.3 Exclusion Criteria

- 1. Available qualified autologous cord blood unit.
- 2. Hypotonic or ataxic cerebral palsy without spasticity.
- 3. Autism and autistic spectrum disorders.
- 4. Hypsarrhythmia.
- 5. Legally blind.
- 6. Intractable seizures causing epileptic encephalopathy.
- 7. Evidence of a progressive neurologic disease.
- 8. Has an active, uncontrolled systemic infection or documentation of HIV+ status.
- 9. Known genetic disease or phenotypic evidence of a genetic disease on physical exam.
- 10. Concurrent genetic or acquired disease or comorbidity(ies) that could require a future allogeneic stem cell transplant.

- 11. Requires ventilatory support, including home ventilator, CPAP, BiPAP, or supplemental oxygen.
- 12. Impaired renal or liver function as determined by serum creatinine >1.5mg/dL and/or total bilirubin >1.3mg/dL except in patients with known Gilbert's disease.
- 13. Possible immunosuppression, defined as WBC <3,000 cells/mL or absolute lymphocyte count (ALC) <1500 with abnormal T-cell subsets.
- 14. Patient's medical condition does not permit safe travel.
- 15. Previously received any form of cellular therapy.

5.4 Research Participant Recruitment and Screening

Patients may be recruited through IRB-approved advertising for the study on the websites of CB banks, parent sponsored websites, the NMDP website, selected cerebral palsy societies, local medical providers, and through a record of inquiries for previous studies (brain injury database. Separate IRB approval will be obtained for any advertisements.

Screening for this study is conducted under a separate, IRB-approved screening protocol (Pro00063563). Under this protocol, after written informed consent is obtained from a parent/guardian, the patient's medical records, videos, and results of brain imaging are obtained and reviewed. The medical review is conducted by a team of pediatric nurses, nurse practitioners, and physicians to identify the presence of any exclusion criteria. If no exclusion criteria are identified, screening labs are performed and a search may be conducted to identify a suitably matched CB unit (see section 6.1).

5.5 Early Withdrawal of Research Participants

Criteria for Removal from Protocol Therapy:

- 1. Diagnosis of a genetic disease while under evaluation or on study.
- 2. Change in medical condition that precludes study participation.

Patients who are off protocol therapy are to be followed until they meet off-study criteria (see below). Follow-up data will be obtained on off-protocol participants unless consent is withdrawn. Participants that are taken off study prior to infusion of the CB will be considered not evaluable and can be replaced with another participant.

Off-Study Criteria:

- 1. Death.
- 2. Lost to follow-up.
- 3. Withdrawal of consent for any further data collection.
- 4. Completion of the final study visit.

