Title:	A Phase I/II Study of Allogeneic Umbilical Cord Blood and Umbilical Cord Tissue-Derived Mesenchymal Stromal Cell Infusions in Children with Cerebral Palsy		
Study Phase:	1/11		
Study Site:	Single site; Duke University, Durham NC		
Study Therapy, Dosage, and Route of Administration:	 (1) Single intravenous infusion of a maximum of 10x10⁷/kg allogeneic umbilical cord blood (CB) cells (2) Three intravenous infusions of 2x10⁶/kg human umbilical cord tissue cells (hCT-MSC), manufactured from allogeneic umbilical cord donors 		
Objectives:	 Primary Objective(s): 1. To determine the efficacy of repeated intravenous doses of hCT-MSC in children with cerebral palsy 2. To determine the effect size of change in GMFM-66 scores in subjects treated with allogeneic CB or hCT-MSC Secondary Objective(s): 1. To determine changes in brain connectivity via MRI imaging in these children and whether they correlate with clinical response 		
Research Participant Population:	: 90 evaluable children ages 2-5 years with hypertonic cerebral palsy due to stroke, periventricular leukomalaci or hypoxic ischemic encephalopathy		
Study Design:	Randomized, open label		
Safety Assessments/Endpoints:	Incidence of infusion reactions, bloodstream infections, graft versus host disease, and alloimmunization		

ABBREVIATIONS

AE	Adverse Event
AlloCB	Allogeneic Umbilical Cord Blood
ASD	Autism Spectrum Disorder
СВ	Umbilical Cord Blood
CBC	Complete Blood Count
CBU	Umbilical Cord Blood Unit
CFR	Code of Federal Regulations
CFU	Colony Forming Unit
CMV	Cytomegalovirus
CRF	Case Report Form
DMSO	Dimethyl Sulfoxide
DTI	Diffusion Tensor Imaging
EMG	Electromyography
FDA	Federal Drug Administration
fMRI	Functional Magnetic Resonance Imaging
GMP	Good Manufacturing Practice
GMFCS	Gross Motor Function Classification System
GMFM-66	Gross Motor Function Measure - 66
GvHD	Graft versus Host Disease
hCT-MSC	Human Cord Tissue-Derived Mesenchymal Stromal Cells
HIE	Hypoxic Ischemic Encephalopathy
HIV	Human Immunodeficiency Virus
HLA	Human Leukocyte Antigen
HTLV	Human T-Cell Lymphotropic Virus
ICH	International Conference on Harmonisation
IRB	Internal Review Board
IV	Intravenous
IVH	Intraventricular Hemorrhage
MCA	Middle Cerebral Artery
MRI	Magnetic Resonance Imaging
MSCs	Mesenchymal Stromal Cells
PVL	Periventricular Leukomalacia
SAE	Serious Adverse Event
STCL	Stem Cell Laboratory
SOP	Standard Operating Procedure
TNCC	Total Nucleated Cell Count
WBC	White Blood Cell

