7.0 STUDY PLAN

7.1 Overview

Parents/Guardians who have previously contacted our program and have a child who may meet eligibility criteria for this study will be notified that this study is available. After initial contact, parents/guardians of potential research participants will have an initial phone interview with study personnel to describe the study, verify basic eligibility criteria, and confirm their interest in participation. The participant's eligibility will then be screened through review of medical records, video, laboratory testing, and imaging under a separate screening protocol.

Once all screening is complete and the patient is likely to meet study criteria, a suitable

unrelated donor CB unit will be identified at the Carolinas Cord Blood Bank, or other accredited cord blood bank. The CB unit will be screened as described in section 6. Participants will then travel to Duke for their first visit. On day 1, written informed consent will be obtained. Patient eligibility will be confirmed by a physical observation and verification of cerebral palsy diagnosis and GMFCS level. If no exclusion criteria are realized, the participant will be randomized to a treatment arm. During their first visit, all participants will have physical therapy evaluations, and a subset of patients will undergo brain MRI. Participants will have study infusions as determined by their assigned treatment arm (at baseline only for AlloCB; at 12-months only for Natural History; at baseline, 3-, and 6-months for MSCs). Participants will be evaluated the day after each infusion. All participants will return to Duke six (motor assessments) and 12 months (motor assessments and brain MRI) after the baseline visit. Participants on the MSC arm will also return at three months for an hCT-MSC infusion. A remote safety assessment will be performed via phone or email at 24 months post-infusion.

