9.6 Subject Replacement

The sponsor may replace any subject who has not been dosed.

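### Do the replacement rules in sections 5.5 and 9.6, worded differently and open longer for controls, put the arm counts or the primary analysis at risk?

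*Combined protocol and SAP*

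**What the plan says.** Two places deal with replacement. Section 5.5 (Early Withdrawal of Research Participants) says: "Participants that are taken off study prior to infusion of the CB will be considered not evaluable and can be replaced with another participant". Its list of off-study criteria includes "Completion of the final study visit", alongside death, loss to follow-up and withdrawal of consent for further data collection. Section 9.6 (Subject Replacement) says: "The sponsor may replace any subject who has not been dosed".

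Section 4.1 sets the infusion schedule. The AlloCB arm has one cord blood infusion at baseline. Of the controls, the Natural History children, it says that they "will not receive an infusion at baseline but will receive an allogeneic CB infusion at 12 months". MSC children have hCT-MSC at months 0, 3 and 6, and no cord blood is scheduled for them.

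The enrolment target is expressed in evaluable children in the synopsis, in section 5.1 ("Ninety evaluable children ages 2-5 years with hypertonic cerebral palsy"), in section 8.2 and in section 8.5 (90 in total, 30 per group). Section 5.5 is the only text that says who is not evaluable in this trial. Section 8.6.1 defines two analysis sets: intention to treat (everyone enrolled and randomised, by assigned arm) and safety (at least one infusion). Section 8.6.4 reports the primary estimates in the former.

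**The concern.** Read literally, section 5.5 closes the replacement window at baseline for AlloCB, at month 12 for Natural History, and never for MSC. Because completing the last visit is itself an off-study criterion, even an MSC child who finishes the study would be not evaluable. Section 9.6 closes the MSC window at the first dose, so the two sections contradict each other for that arm.

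A second asymmetry does not depend on wording. Controls are undosed for the whole 12-month outcome period, so under either rule they can be replaced throughout it, while treated children normally cannot be after their first infusion. The trial is open label and replacement is optional, so the decision is taken with the allocation known.

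At stake would be who counts toward 30 per group, when enrolment may stop, and whether discretionary replacement could tilt the comparison between arms. Nor does the plan say in so many words whether a replacement inherits the lost child's arm or is randomised afresh.

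**Working it through.** **The two rules by arm.** Months of the 12-month outcome period in which a child may be replaced, with infusions given on schedule (4.1):

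| Arm | First cord blood | First dose of any product | 5.5 as worded | 9.6 |
|---|---|---|---|---|
| AlloCB | baseline | baseline | 0 | 0 |
| Natural History | month 12 | month 12 | 12 | 12 |
| MSC | never | baseline | 12 | 0 |

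The rules differ in one cell pair, MSC. If cord blood in 5.5 is read as study product, the MSC entry becomes 0 and the sections agree. Section 7.5 narrows its wording in the same way: its text on reactions during infusion mentions only the cord blood infusion, although MSC children are infused too. The zeros are not absolute: section 7.4 postpones an infusion for illness, and the window stays open until the dose is given.

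**Who is in the primary analysis.** Section 8.6.1 admits every randomised child, with no condition on infusion, evaluability or replacement. A child labelled not evaluable under 5.5 stays in, with whatever scores were recorded. A control lost before month 12 has no 12-month score whether or not a replacement is enrolled.

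**How often the label and the data could disagree.** A control with a month-12 GMFM-66 who is then not evaluable under 5.5 must go off study between that assessment and an infusion due at the same time point (7.1, 7.9). Declining or postponing the infusion meets none of the off-study criteria.

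**The plan's sample size.** Section 8.5 iterates N = (t × s / E)², with s = 5.16 and E = 2. With unrounded t:

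- N = 20: t = 2.093, giving 29.16, so 29
- N = 29: t = 2.048, giving 27.93, so 28
- N = 28: t = 2.052, giving 28.02, so 28

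The stated 28 per group is reproduced with rounding to the nearest whole number, and 30 are planned.

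**Cost of closing the control window.** Section 8.5 has no dropout allowance, so replacement is what protects the margin. The documents give no loss rate; the range below is assumed. Margin = t(0.975, n−1) × 5.16 / √n.

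| Assumed loss in an arm of 30 | n left | Margin (points) | Randomised to keep 30, i.e. 30/(1 − loss) rounded up |
|---|---|---|---|
| 0% | 30 | 1.93 | 30 |
| 5% | 28 | 2.00 | 32 |
| 10% | 27 | 2.04 | 34 |
| 15% | 25 | 2.13 | 36 |
| 20% | 24 | 2.18 | 38 |

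**Timeline.** Accrual of up to 15 months puts the last 12-month visit at 15 + 12 = 27 and the last contact at 15 + 24 = 39, as section 8.3 states. One control replaced as late as month 27 would move these to 27 + 12 = 39 and 27 + 24 = 51. That illustrates an optional act that the sponsor need not take.

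**Arm of a replacement.** Section 5.5 speaks of another participant, and section 8.1 randomises participants 1:1:1 within strata. Section 7.1 says of an eligible child: "If no exclusion criteria are realized, the participant will be randomized to a treatment arm". Nothing provides for direct assignment to an arm. Under independent simple draws a lost control would be refilled by a control with chance 1/3, or three new children on average. The plan stratifies and does not describe how the list is generated, so that figure cannot be applied to it.

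**The case for a change.** The strongest case is that this is more than a slip. Correcting 5.5 to mean study product leaves the control asymmetry untouched. Section 9.6 does not even require that the child be off study, so on its face it reaches a control still in follow-up. Evaluable governs when enrolment stops, yet it refers to an infusion and not to having a 12-month GMFM-66. The analysis waits for the last child's 12-month visit (8.6.2), so a late replacement delays it. Rewording would be cheap, and 28 per group is enough for the plan's own calculation.

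The textual points stand: 5.5 does not fit the MSC arm, the control window is longer, and evaluable has no positive definition. The inference to harm does not. Even the broadest reading of 9.6 lets the sponsor add a child without removing the one replaced. The obvious remedy, closing every window at the end of the baseline visit, would not remove discretion under open allocation, because randomisation comes on day 1 (7.1) or before travel (7.2). It could also make a dosed child replaceable, since section 7.9 lists the day-after-infusion check under baseline. And the slack between 30 and 28 covers about a 5% loss and no more.

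**Conclusion.** No change follows. The contradiction between 5.5 and 9.6 is confined to the MSC arm and is most plausibly a clerical slip. Nobody would treat an MSC child who completes the study as not evaluable, and 9.6 supplies the workable rule. The missing definition of evaluable is a gap that analysts fill sensibly: the interval in section 8.5 can only be computed from children with the scores it needs, and the intention-to-treat text fixes who is included. The longer window for controls is a fair trade-off. It lets the sponsor restore an arm that has lost 12-month scores, in a design with no dropout allowance, at the price of an asymmetry between arms and a possible delay. Giving it up would move the margin from 1.93 points to 2.04 at 27 per arm or 2.13 at 25, past the 2-point target.

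This rests on three assumptions: that replaced children stay in the intention-to-treat set, as 8.6.1 says of all randomised participants; that replacements are randomised as 8.1 describes; and that control losses are few. No loss rate is given, so the 10% and 15% behind those margins are illustrative. No bias in the primary estimates has been shown.
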